An Adjudication Committee will be utilized to confirm the diagnosis and overall, clinical, radiological and mycological response of IA or IM.

V. FLOW CHART AND SCHEDULE OF ASSESSMENTS

Figure 1 Flow Chart

EOT: end of treatment; IA: invasive aspergillosis; IM: invasive mucormycosis

Table 1 Schedule of Assessments (IA and IM Subjects) – Screening through Day 84 and IA Follow-up (30 and 60 Days Post-Day 84 or EOT [Last Dose of Study Drug])

Period	Screening	1	Treatment														IA Follow-up ²	
			2	3	7	14	21	28	35	42	49	56	63	70	77	84 or IA EOT ¹	110 (30 Day) IA or EOS	Day 140 (60 Day) IA or EOS
Day	-5 to 1 (predose)																	
Visit window (days)	none	none	none	none	± 2	± 2	± 2	± 2	± 2	± 2	± 2	± 2	± 2	± 2	± 2	± 7	± 7	± 7
ASSESSMENTS																		
Informed consent/assent	X																	
Verify eligibility criteria	X	X																
Demographics	X																	
Medical/surgical history	←																	→
EORTC/MSG diagnosis ³	←																	
Physical examination	X															X		
Height and weight ⁴	X															X		
Vital signs ⁵	X	X	X	X	X	X	X	X	X	X	X	X	X	X	X	X		
Routine 12-lead ECG ⁶	X	X			X	X		X				X				X		
Serum or BAL galactomannan	X																	
Efficacy response assessment ⁷	←																	→
Pharmacokinetic trough sampling ⁸					X	X	X			X						X		
Pharmacokinetic 24-hour sampling ⁹						X												
Clinical laboratory tests (chemistry, INR, hematology) ¹⁰	X				X			X				X				X		
Hepatic panel ¹¹	X			X	X	X	X	X	X	X	X	X	X	X	X	X		
Pregnancy test ¹²	X							X		X						X		
Prior and concomitant medications ¹³	←																	→
AE ¹⁴	←																	→
Isavuconazonium sulfate dosing ¹⁵		q8h	q8h	X	X	X	X	X	X	X	X	X	X	X	X	X		
Oral dosing acceptability assessment		X ¹⁶																
Mortality Status ¹⁷											X					X		

AE: adverse event; BAL: bronchoalveolar lavage; ECG: electrocardiogram; EORTC/MSG: European Organisation for Research and Treatment of Cancer/Mycoses Study Group; EOS: end of study; EOT: end of treatment; IA: invasive aspergillosis; IM: invasive mucormycosis; INR: international normalized ratio; q8h: once every 8 hours.

Footnotes continued on next page

1. If subject discontinues study drug prior to day 84 for IA subjects, all EOT procedures must be completed. If subject continues to allow consent, EOS information to be collected on follow-up.

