11. Hepatic panels will be collected at baseline, day 3, day 7 and then weekly thereafter while subjects are receiving study drug.
12. Pregnancy testing not applicable for male subjects. Not necessary for female subjects who are of non-childbearing potential (e.g., premenarchal in the judgment of the investigator on day 1 and throughout the study treatment, or documented surgically sterile). Pregnancy testing may be urine or serum, dependent upon institutional standard of care.
13. Concomitant medications are to be captured during the study and only related to AE's during the 30- and 60-day follow-up period.
14. All AEs must be monitored until symptom resolution or until the condition stabilizes.
15. For both intravenous and oral dosing: Loading doses on days 1 and 2 will be administered every 8 (\pm 2) hours. The first maintenance dose should start 12 to 24 hours after the administration of the last loading dose. Subsequent maintenance doses will be administered once daily (24 \pm 2 hours from the previous maintenance dose). Subjects who are discharged from the hospital with oral capsules for at-home administration must return weekly to receive new oral dosing supplies. Return visits should coincide with days when study-related assessments are required. Oral dosing is allowed for subjects 6 to $<$ 18 years of age and with a body weight of at least 12 kg.

Footnotes continued on next page

16. Subjects who begin oral administration are to complete the oral dosing acceptability assessment after ingesting their first oral dose.
17. All-cause Mortality will be assessed on days 42 and 84 or EOT.

Table 2 Extended Schedule of Assessments (IM Subjects) – Day 85 through Day 180 and IM Follow-up (30 and 60 days Post-Day 180 [Last Dose of Study Drug])

Period	Treatment				Follow-up ²		
	Day	85	115	145	180/IM or EOT ¹	210 (30 Day) IM or EOS	240 (60 Day) IM or EOS
Visit window (days)	± 2	± 2	± 2	± 7	± 7	± 7	± 7
ASSESSMENTS							
Physical examination					X		
Weight					X		
Vital signs ³	X	X	X	X			
Routine 12-lead ECG ⁴	X	X	X	X			
Efficacy response assessment ⁵	◀					▶	
Clinical laboratory tests (chemistry, hematology, hepatic panel, INR) ⁶		X	X	X			
Pregnancy test ⁷					X		
Prior and concomitant medications ⁸	◀					▶	
AE ⁹	◀					▶	
Isavuconazonium sulfate dosing ¹⁰	X	X	X	X			
Oral dosing acceptability assessment	X ¹¹						
Mortality Status ¹²					X		

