AE: adverse event; EOS: end of study (30 days post-last dose); EOT: end of treatment (60 days post-last dose); IA: invasive aspergillosis; IM: invasive mucormycosis; INR: international normalized ratio

1. If subject discontinues study drug prior to day 180 for IM subjects, all EOT procedures must be completed. If subject continues to allow consent, EOS information to be collected on Follow-up.
2. Follow-up is to be completed 30 days (± 7) and 60 days (± 7) post-last dose from day 180/EOT for IM subjects; may be performed via telephone at the discretion of the investigator.
3. Vital signs are to be measured within 1 hour prior to and approximately 1 hour after the end of each infusion. No additional vital signs are needed on dosing days for oral administration.
4. 12-lead ECG will be performed prior to study drug administration on each scheduled day.
5. Record assessments that are performed during the study to document response to antifungal therapy (e.g., serum galactomannan, radiology, mycological tests, changes in clinical signs and symptoms and any surgical procedures).
6. Clinical (safety) laboratory samples will be assessed by the local laboratory. Clinical laboratory tests (chemistry, hematology, hepatic panel and INR) to be drawn monthly.

Footnotes continued on next page

7. Pregnancy testing not applicable for male subjects. Not necessary for female subjects who are of non-childbearing potential (e.g., premenarchal in the judgment of the investigator on day 1 and throughout the study treatment, or documented surgically sterile).
8. Concomitant medications are to be captured during the study and only related to AE's during the 30- and 60-day follow-up period.
9. All AEs must be monitored until symptom resolution or until the condition stabilizes.
10. For both intravenous and oral dosing: Subsequent maintenance doses will be administered once daily (24 ± 2 hours from the previous maintenance dose). Subjects who are discharged from the hospital with oral capsules for at-home administration must return weekly to receive new oral dosing supplies. Return visits should coincide with days when study-related assessments are required. Oral dosing is allowed for subjects 6 to < 18 years of age and with a body weight of at least 12 kg.
11. Subjects who begin oral administration are to complete the oral dosing acceptability assessment after ingesting their first oral dose.
12. All-cause Mortality will be assessed at day 180 or EOT.

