1.4 Risk Benefit Assessment

The safety of isavuconazonium sulfate in pediatric subjects has been investigated in a study with a total of 27 subjects. In this small study, isavuconazonium sulfate appeared to be generally well-tolerated with a safety profile similar to that observed in adults. The efficacy of isavuconazonium sulfate in pediatric subjects has not yet been studied. It is expected that the dosage regimen used in the study will result in efficacious exposures in pediatric subjects and therefore subjects will likely benefit from participating in this study.

Subjects enrolled in this study may experience AEs, including previously unknown AEs related to study drug or may experience procedural complications (e.g., bruising from blood draws and slight skin irritation from the adhesive on the electrocardiogram [ECG] electrodes). While the proposed dosage regimen was established to minimize the number of subjects reaching exposures associated with increased toxicity in adults, some pediatric subjects could reach exposures that resulted in central nervous system and GI-type adverse effects in adults. Subjects with familial short QT syndrome are excluded from participation in this study. Pediatric subjects enrolled in this study will be closely monitored for AEs, especially for liver toxicity. Overall, based on the target population selected for this study, the exclusion criteria and the proposed dosage regimen, which matches adult efficacious exposures, the benefit and risk assessment associated with the participation of pediatric subjects in this clinical study is favorable.

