5.8 Total Amount of Blood

The total blood volume to be collected on subjects 1 to < 18 years of age for the study through day 84 or EOT should not be more than 45 mL. Table 7 provides the amount of blood drawn for each laboratory parameters and study visit for these subjects.

Table 7 Total Amount of Blood Drawn

Parameter	Study Visit						Total Volume
	Screening	Labs: Days 7, 28, 56 and 84 or EOT	Pharmacokinetics: Days 7, 14, 21, 42 and 84 or EOT	Days 3, 14, 21, 35, 42, 49, 63, 70 and 77	IV Pharmacokinetics: 24-hour Sampling Day Anytime Between Days 14 and 42	Oral Pharmacokinetics: 24-hour Sampling Day Anytime Between Days 14 and 42	
Hematology	2 mL	2 mL/visit (8 mL)	N/A	N/A	N/A	N/A	10 mL
Chemistry	2 mL	2 mL/visit (8 mL)	N/A	N/A	N/A	N/A	10 mL
Hepatic Panel	*	*	N/A	1 mL/visit (9 mL)	N/A	N/A	9 mL
Serum GM	2 mL	N/A	N/A	N/A	N/A	N/A	2 mL
Pharmacokinetics	N/A	N/A	1 mL/visit (5 mL)	N/A	1 mL/time point (4 mL)	1 mL/time point (7 mL)	9 mL or 12 mL
PT/INR	1 mL	1 mL/visit (4 mL)	N/A	N/A	N/A	N/A	5 mL
TOTAL	7 mL	20 mL	5 mL	9 mL	4 mL	7 mL	45 mL (IV 24-hr PK) -OR- 48 mL (Oral 24-hr PK)

EOT: end of treatment; GM: galactomannan; INR: international normalized ratio; IV: intravenous; N/A: not applicable; PK: pharmacokinetics; PT: prothrombin time

* Included with chemistry

The total blood volume to be collected on IM subjects 1 to < 18 years of age during the IM follow-up period should not be more than 15 mL. Table 8 provides the amount of blood drawn for each laboratory parameters for these subjects.

Table 8 Blood Drawn During IM Follow-up

Parameter	Study Visits Days 115, 145 and 180 or EOT	Approximate Total Volume
Hematology	2 mL/visit (6 mL)	6 mL
Chemistry	2 mL/visit (6 mL)	6 mL
Hepatic Panel	*	N/A
PT/INR	1 mL/visit (3 mL)	3 mL
TOTAL	15 mL	15 mL

*Hepatic panel to be drawn with chemistry panel.

INR: international normalized ratio; PT: prothrombin time

Regarding the protocol-specified clinical laboratory, if clinical safety laboratory results are already available, these data are sufficient for monitoring safety as per the protocol and must be recorded in the eCRF. In order to minimize blood draws, it is not necessary to draw an additional sample for the sole purposes of the clinical trial.

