Severe hepatic liver function abnormalities as defined above, in the absence of another etiology, may be considered an important medical event and may be reported as a SAE. The sponsor should be contacted and informed of all subjects for whom severe hepatic liver function abnormalities possibly attributable to study drug are observed.

To further assess abnormal hepatic laboratory findings, the investigator is expected to:

- Obtain a more detailed history of symptoms and prior or concurrent diseases. Symptoms and new-onset diseases is to be recorded as “AEs” within the eCRF. Illnesses and conditions such as hypotensive events, and decompensated cardiac disease that may lead to secondary liver abnormalities should be noted. Nonalcoholic steatohepatitis is seen in obese hyperlipoproteinemic and/or diabetic subjects, and may be associated with fluctuating AT levels. The investigator should ensure that the medical history form captures any illness that predates study enrollment that may be relevant in assessing hepatic function.
- Obtain a history of concomitant drug use (including nonprescription medication, complementary and alternative medications), alcohol use, recreational drug use and special diets. Medications, is to be entered in the eCRF. Information on alcohol, other substance use and diet should be entered on the LA-CRF or an appropriate document.
- Obtain a history of exposure to environmental chemical agents.
- Based on the subject’s history, other testing may be appropriate including:
 - Acute viral hepatitis (A, B, C, D, E or other infectious agents),
 - Ultrasound or other imaging to assess biliary tract disease,
 - Other laboratory tests including INR, direct bilirubin.
- Consider gastroenterology or hepatology consultations.
- Submit results for any additional testing and possible etiology on the LA-CRF or an appropriate document.

Study Treatment Discontinuation

In the absence of an explanation for increased LFT’s, such as viral hepatitis, preexisting or acute liver disease or exposure to other agents associated with liver injury, the subject may be discontinued from study treatment. The investigator may determine that it is not in the subject’s best interest to continue study treatment. Discontinuation of study treatment should be considered if:

- ALT or AST $> 8 \times$ ULN.
- ALT or AST $> 5 \times$ ULN for more than 2 weeks.

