6 STATISTICAL METHODOLOGY

6.1 General Considerations

Continuous data will be summarized descriptively including the number of subjects (n), mean, standard deviation (SD), median, minimum and maximum. Categorical data will be summarized by frequencies and percentages with 95% confidence interval (CI). Efficacy data will be summarized by type of infection including IA, IM and mixed IA/IM infected subjects. Safety summaries will also be presented for by type of infection. The IA group will comprise subjects with IA infection without known IM infection; the IM group will comprise subjects with IM without known IA infection; and the IA/IM group will comprise subjects with mixed IA/IM infection. Analysis Windows will be used and, for those parameters with weekly data collection, are illustrated below in Section 6.9. For those parameters collected less often appropriate windows will be defined. Note that, IM and IA/IM infected subjects will be reported to conclusion of treatment and 60 day follow-up although day 180 is not considered an endpoint analysis. Kaplan Meier (K-M) analyses for mortality will incorporate all survival data to day 240 if IM subjects are included.

All data summarization and analyses will be performed using SAS® Version 9.1.3 or higher. Specifications for table, figures and data listing formats can be found in the Tables, Listings, and Figures (TLF) specifications.

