6.5.2 Clinical Laboratory Evaluation

Clinical laboratory samples will be collected and reported based on timepoints as listed in the Protocol Table 1 and Table 2 in Section 1 based on lab sample collection visits.

Clinical Laboratory variables will be created for each of the following:

| Chemistry: | Hematology: |
|--|--|
| Sodium | Red blood cells |
| Potassium | White blood cells (total leukocytes) |
| Magnesium | Hemoglobin |
| Calcium | Hematocrit |
| Chloride | Platelets (thrombocytes) |
| Glucose | Neutrophils (ANC) |
| Creatinine | Eosinophils |
| Creatine phosphokinase/Creatine kinase | Basophils |
| Alkaline phosphatase (ALP) | Lymphocytes |
| | Monocytes |
| | Blast cells |
| Hepatic Panel: | Pregnancy Test: |
| Albumin | Human chorionic gonadotropin (hCG) |
| Total bilirubin (TBL) | |
| Direct Bilirubin | |
| Total Protein | |
| Alanine aminotransferase (ALT) | |
| Aspartate aminotransferase (AST) | |
| | Other: |
| | Serum galactomannan (GM) |
| | Partial thromboplastin time/international normalized ratio (PTT/INR) |

The baseline value will be the last non-missing value taken on or prior to first dose of study drug. Quantitative values evaluated by the central laboratory including hematology and biochemistry will be summarized using mean, standard deviation, minimum, maximum and median at each analysis visit. Additionally, a within-subject change will be calculated as the post-baseline measurement minus the baseline measurement and summarized in the same

way. Clinical Laboratory data will be reported using the SAF population by Clinical Laboratory Tests collected at baseline and days 7, 28, 56 and 84 (or EOT).

Shifts relative to normal ranges from baseline to each time point during treatment period in lab tests will also be tabulated. Laboratory data will be displayed in listings. For quantitative laboratory measurements descriptive statistics will be used to summarize results and change from baseline for subjects.

Each laboratory result will be classified as low, normal, or high at each visit according to the laboratory supplied reference ranges as specified in the Protocol.

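### Weekly and monthly hepatic-panel wordings are not reconciled for mucormycosis subjects dosed after Day 84, and the SAP 6.5.2 laboratory day list contradicts its own section and, read literally, omits most hepatic panels

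*Protocol*

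**What the plan says.** **Protocol, schedule.** Table 1 applies to IA and IM subjects, and its title limits it to "Screening through Day 84 and IA Follow-up". Its hepatic-panel row is marked at screening, Day 3, Day 7 and every week to Day 84. Footnote 11 to that row reads: "Hepatic panels will be collected at baseline, day 3, day 7 and then weekly thereafter while subjects are receiving study drug". IM subjects may be dosed to Day 180 (Section 2.2.1). For Days 85 to 180, Table 2 places the hepatic panel in the general laboratory row, marked on Days 115, 145 and 180 or EOT, and footnote 6 says "Clinical laboratory tests (chemistry, hematology, hepatic panel and INR) to be drawn monthly". Table 8 in Section 5.8 budgets blood under the column "Study Visits Days 115, 145 and 180 or EOT", 15 mL in all.

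**Protocol, liver criterion.** The synopsis (Formal Stopping Rules) and Appendix 12.5 list "ALT or AST $> 5 \times$ ULN for more than 2 weeks" among the findings for which stopping treatment should be considered. Section 6.1 only points to Appendix 12.5. That appendix also asks for a retest within 72 hours once aminotransferases exceed 3 × ULN or bilirubin exceeds 2 × ULN, and then testing 2 to 3 times weekly for a confirmed moderate abnormality.

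**SAP.** Section 6.5.2 opens by tying laboratory reporting to the time points of Protocol Tables 1 and 2. It later asks for shifts at every on-treatment time point, as does Protocol 7.5.2. Between those two statements it reports laboratory data in the SAF "population by Clinical Laboratory Tests collected at baseline and days 7, 28, 56 and 84 (or EOT"). SAP 6.1 says that "IM and IA/IM infected subjects will be reported to conclusion of treatment and 60 day follow-up". SAP 6.5.3 takes each subject's highest value up to Day 84 (IA), Day 180 (IM) or EOT.

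**The concern.** There are two separate problems.

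The first is in the protocol. Footnote 11 makes the weekly panel depend on receiving drug, not on a day number. An IM child on Day 100 is receiving drug, so that footnote says weekly while Table 2 says monthly. Even if the monthly schedule is the intended one, the protocol does not say how a criterion defined by more than 2 weeks' duration is to be evaluated from draws a month apart. The protocol itself gives the topic weight: Section 1.4 says "Pediatric subjects enrolled in this study will be closely monitored for AEs, especially for liver toxicity", and Section 1.2 reports that raised liver enzymes, judged drug-related, led to one of the two withdrawals for adverse events in the earlier pediatric study.

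The second is in the SAP. A programmer who follows the day list in 6.5.2 produces different laboratory tables from one who follows the sentences around it. On the day list, most scheduled hepatic panels would not appear in the by-visit summaries of a trial whose first objective is safety.

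**Working it through.** **1. The plan's own figures.** Table 8: 3 draws × (2 + 2 + 1) mL = 15 mL, as stated. Table 7 (IV sampling): 10 + 10 + 9 + 2 + 9 + 5 = 45 mL, as stated, where the first 9 is 9 hepatic-only days × 1 mL. Both reproduce, so the monthly schedule after Day 84 is budgeted consistently.

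**2. Can both wordings be followed?** Weekly panels after Day 84 would fall on Days 91, 98, …, 175: (175 − 91)/7 + 1 = 13 draws. At Table 7's 1 mL per hepatic-only draw (assumed to carry over), the total is 15 + 13 = 28 mL. If the two draws within 3 days of Day 115 or 145 (Days 112 and 147) are merged with those visits, it is 15 + 11 = 26 mL. Either figure exceeds the 15 mL limit, unless local results are already available, which Section 5.8 accepts without a further draw.

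**3. Gaps between scheduled panels, IM after Day 84.** Visit windows from Tables 1 and 2 are ±7, ±2, ±2 and ±7 days for Days 84, 115, 145 and 180.

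| Interval | Gap (days) | Shortest | Longest |
|---|---|---|---|
| 84 to 115 | 31 | 31 − 7 − 2 = 22 | 31 + 7 + 2 = 40 |
| 115 to 145 | 30 | 30 − 2 − 2 = 26 | 30 + 2 + 2 = 34 |
| 145 to 180 | 35 | 35 − 2 − 7 = 26 | 35 + 2 + 7 = 44 |

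Every gap exceeds 14 days even at its shortest.

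**4. Chance that an elevation meets a scheduled draw.** If onset is uniform over a gap of g days and the episode lasts L days, the chance is min(1, L/g).

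| L (days) | g = 30 | g = 31 | g = 35 |
|---|---|---|---|
| 15 | 50% | 48% | 43% |
| 21 | 70% | 68% | 60% |
| 28 | 93% | 90% | 80% |

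Under footnote 11's 7-day spacing a 15-day episode always contains at least two draws. The two wordings therefore differ materially in what they can show. The comparison does not say which one is appropriate.

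**5. Panels kept by the SAP day list.** Scheduled post-baseline hepatic days to Day 84 are 3, 7, 14, 21, 28, 35, 42, 49, 56, 63, 70, 77 and 84, which is 13. The list keeps 7, 28, 56 and 84, which is 4. It omits 9 of 13 (69%), exactly the nine hepatic-only days of Table 7. For an IM subject dosed to Day 180 there are 16 panels: 12 of 16 (75%) are omitted, or 11 of 16 (69%) if Day 180 counts as EOT.

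**The case against.** **The frequency conflict is one of scope.** Table 1 ends at Day 84 for treatment visits, Table 2 has its own explicit footnote, and Table 8 budgets exactly the Table 2 draws. This is a fair reading and probably the intended one. What remains is that footnote 11 states no end day and sets a condition, receipt of drug, that continues past Day 84.

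**The 2-week criterion still works.** A reader might infer from the monthly gaps that the criterion cannot operate. The documents do not support that. Any value above 3 × ULN triggers a 72-hour retest, and a confirmed moderate abnormality is then tested 2 to 3 times weekly, so duration can be followed once an elevation is found. The criterion is also one of several and calls for consideration, not mandatory stopping. What remains is first detection: the retesting starts only after an abnormal value has been drawn.

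**IM subjects are not the least monitored.** That too might be inferred, but an IM subject dosed to Day 180 has the same 13 panels to Day 84 as an IA subject, plus three more. Only the rate falls after Day 84.

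**The SAP still uses the other panels.** The day list matches Table 1's chemistry, INR and hematology row and may have been meant only for that row. Appendix 1 of the SAP has windows for Day 3, every weekly visit and Days 115, 145 and 180. Section 6.5.3 analyses each subject's maximum to Day 180 for IM and plots all patients, and all laboratory data are listed. A claim that liver safety in extended dosing would rest on almost no summarised data is therefore not supported. However, 6.5.2 names the hepatic panel among its variables and gives it no visit list of its own, so the day list is the only explicit one. A maximum-value table also does not show timing or duration.

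**The detection figures are simplified.** They assume uniform onset and no unscheduled or local testing, and this population may well have such tests.

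**Conclusion.** The point holds as two wording defects.

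First, footnote 11 is not reconciled with Table 2 footnote 6 and Table 8 for IM subjects on drug after Day 84. On the scheduled draws alone, with gaps of 30 to 35 days and never under 22, an elevation above 5 × ULN lasting more than 2 weeks can be missed or found late. A 15-day episode meets a draw with probability 43% to 50% under uniform onset and no other testing. This concerns only IM subjects dosed beyond Day 84, a number the documents do not give.

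Second, the SAP 6.5.2 day list contradicts its own section, SAP 6.1 and Protocol 7.5.2. Taken literally and applied to the hepatic panel, it removes 9 of 13 post-baseline panels to Day 84 from the visit summaries for all subjects, and Days 115 and 145 for IM. The data are not lost: the maximum-value analysis and listings retain them.

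Nothing here shows that monthly or weekly panels are right or wrong. That is a clinical decision for the sponsor.

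**What to change.** 1. **SAP 6.5.2.** Replace the day list with all scheduled laboratory and hepatic-panel days of Protocol Tables 1 and 2, including Days 115, 145 and 180/EOT for IM and mixed IA/IM subjects. Cost: one sentence and additional rows in the by-visit tables. No new data are needed.
2. **Protocol.** Reconcile Table 1 footnote 11, Table 2 footnote 6, Table 8 and Appendix 12.5. State which hepatic-panel schedule governs which dosing days, and how the 2-week criterion is evaluated under it, including from which value the duration is counted. Cost: footnote and appendix wording at the next amendment. Table 8 needs updating only if the reconciled schedule differs from the one it budgets.
3. **Protocol Table 2 or Section 5.4.2.** State that local hepatic results obtained between Day 85 and EOT are entered in the eCRF. Section 5.4.2 already accepts and records available results in place of protocol-specified tests. This would make clear that results between the scheduled days count too. Cost: some data entry for the IM subjects dosed beyond Day 84, and no extra blood.
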